7.1 Full Analysis Set

The Full Analysis Set (FAS) will include all randomized subjects who received at least one dose of study treatment. Subjects will be included in the analysis according to the treatment to which they were randomized.

7.2 Per Protocol Set

The PPS will include all randomized subjects who:

- Received all four injections of study treatment
- Have a non-missing BCVA ETDRS result at Week 16
- Were not discontinued prior to Week 16 for any reason
- Have not experienced any major protocol deviations that have the potential to impact the efficacy results.

Subjects will be included in the analysis according to the treatment received.

7.3 Safety Set

[figure not shown]
The Safety Set (SAF) will include all randomized subjects who received at least one dose of study treatment. Subjects will be included in the analysis according to the treatment received.

8. General Statistical Considerations

8.1 Unit of Analysis

Ophthalmic safety endpoints will be analyzed for both eyes. Non-ophthalmic safety endpoints will be analyzed with subject as the unit of analysis. For efficacy endpoints, the unit of analysis will be the study eye.

The study eye will be defined as the eye that meets all of the inclusion and none of the exclusion criteria. If both eyes qualify, the eye with the worse BCVA ETDRS at Day 1 will be used as the study eye. If both

eyes have the same BCVA ETDRS at Day 1, the eye with the highest CST on SD-OCT on Day 1, as assessed by the Investigator, will be used as the study eye. If both eyes qualify and neither is preferred based on the inclusion/exclusion criteria and have the same BCVA ETDRS and CST on Day 1, either eye may be chosen as the study eye. In this instance, the Investigator should select the eye that, in their opinion, is most likely to respond to treatment as the study eye.

8.2 Missing Data Conventions

Partial/missing start and end dates for AEs and concomitant medications will be imputed to create complete dates for the determination of treatment-emergent AEs or medications concomitant with study treatment.

Partial/missing start dates:

- Dates with missing day only will be imputed as the 1st of the month unless the month and year are same as the month and year of first dose of study medication, in which case missing day will be imputed as the first dose day of study medication.
- Dates with both day and month missing will be imputed as 1 Jan unless the year is same as the year of first dose of study medication, in which case missing day and month will be imputed as the first dose day and month of study medication.
- Completely missing dates will be imputed as the first dose date of study medication unless the end date is on or before the first dose date of study medication, in which case missing date will be imputed as 1 Jan of the same year as the end date.

Partial/missing end date:

- Dates with missing day only will be imputed as the last day of the month unless the month and year are the same as the month and year of the last dose of study medication, in which case missing day will be imputed as the last dose day of study medication.
- Dates with both day and month missing will be imputed as 31 Dec unless the year is same as the year of the last dose of study medication, in which case missing day and month will be imputed as the last dose day and month of study medication.
- If the ongoing flag is missing or “Yes” then the date will not be imputed unless death date is available, in which case the missing date will be imputed as the death date.
- If the imputed date is after the date of death, then the end date will be set equal to the date of death.

The original dates will be displayed in data listings and the imputed dates will be used in derivations only (study day, treatment-emergence status, etc.).

The primary and secondary efficacy data analyses will be performed on the FAS [REDACTED]. An analysis using observed data only will also be performed in both the FAS and PPS. [REDACTED] will be used to impute missing data in the FAS for the analysis of the primary and secondary continuous efficacy variables. No exploratory efficacy endpoints or safety endpoints will be imputed.

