14.1 Adverse Events

An AE is defined as any untoward medical occurrence associated with the use of an investigational product (IP) in humans, whether or not considered IP-related. AEs starting on or after the date of first exposure to study drug and up to 28 days after last injection will be considered treatment-emergent adverse events (TEAEs). AEs with unknown onset dates will be counted as a TEAE. All AEs will be assigned a severity grade of mild, moderate, or severe. Their relationship to study drug will be classified as suspected or not suspected. TEAEs with a missing relationship to study treatment will assume greatest relationship to study treatment (suspected). Only suspected TEAEs are considered as treatment-related. TEAEs with missing severity grades will be categorized as severe for tabulation of TEAEs by severity. The expectedness of an AE will be classified as unexpected, expected or not applicable (not applicable for AEs unrelated to IP). Documentation of AEs will include onset date, location (right eye [OD], left eye [OS], both eyes [OU], not ocular), severity, action(s) taken, relationship to study drug, expectedness, outcome, resolution date, and seriousness. All AEs will be coded using MedDRA classifications with reference to SOCs and PTs (MedDRA version 20.1).

An AE is considered serious if, in the view of either the investigator or sponsor, it results in any of the following outcomes:

- Death
- A life-threatening AE
- Inpatient hospitalization or prolongation of existing hospitalization

- A persistent or significant incapacity or substantial disruption of the ability to conduct normal life functions
- A congenital anomaly/birth defect
- Medically Significant.

Important medical events that may not result in death, be life-threatening, or require hospitalization may be considered serious when, based upon appropriate medical judgment, they may jeopardize the subject and may require medical or surgical intervention to prevent one of the outcomes listed above.

Overall summaries of AEs will be presented showing:

- Number of AEs and number of subjects with any AEs;
- Number of TEAEs and number of subjects with any TEAEs;
- Number of treatment-related TEAEs and number of subjects with any treatment-related TEAEs;
- Number of SAEs and number of subjects with any SAEs;
- Number of treatment-emergent SAEs and number of subjects with any treatment-emergent SAEs;
- Number of subjects with TEAEs leading to premature discontinuation;

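### SAP 8.2 can turn an adverse event that ended before the first injection into a TEAE, and it disagrees with SAP 14.1 on unknown onset dates

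*SAP*

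**What the plan says.** SAP 8.2 (Missing Data Conventions) completes partial and missing AE dates so that treatment emergence can be determined. Listings keep the original dates.

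- **Start, day missing.** The first of the month, except in the month and year of first dose, "in which case missing day will be imputed as the first dose day of study medication".
- **Start, day and month missing.** 1 January, except in the year of first dose, "in which case missing day and month will be imputed as the first dose day and month of study medication".
- **Start completely missing.** The first-dose date, "unless the end date is on or before the first dose date of study medication". When that exception applies, the start becomes 1 January of the year in which the event ended. This is the only start rule that refers to the end date.
- **End, day missing.** The last day of the month, except in the month of last dose, "in which case missing day will be imputed as the last dose day of study medication". A year-only end date in the year of last dose is handled in the same way. The death date is the only limit placed on an imputed end date.

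SAP 14.1 (Adverse Events) defines a TEAE by its start: on or after first exposure and up to 28 days after the last injection. It adds, without exception, "AEs with unknown onset dates will be counted as a TEAE".

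AEs are recorded from the signing of consent (Protocol Table 2, footnote c, repeated in SAP Appendix A), and screening lasts up to 4 weeks (SAP 3.2).

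**The concern.** Events before dosing are collected, so some AEs will begin and end during screening. If the start of such an event is only partly recorded, the two partial-start rules place it on the first-dose date even when a complete end date shows that it was already over. The event is then a TEAE, and its imputed start is later than its recorded end. An event with no start date at all is protected from this under 8.2, so a more fully recorded event is handled worse than a less fully recorded one.

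For completely missing starts the two sections give different answers for the same event, and neither says which prevails. Two programmers, each following one section, would produce different TEAE counts. What is at stake is the accuracy of the TEAE-based safety tables in a trial with 41 subjects per arm.

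**Working it through.** **1. Worked case, partial start.** Assume first dose on 20 June 2018, start recorded as June 2018 without a day, and end on 5 June 2018.

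- Month and year match first dose, so 8.2 sets the start to 20 June 2018.
- 20 June is on or after first exposure and inside the 28-day limit, so 14.1 makes it a TEAE.
- The event ended 20 − 5 = 15 days before first dose, and its imputed start is 15 days after its end.
- If only the year 2018 is recorded, the result is the same.

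**2. Completely missing start: the two sections side by side.**

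| Recorded end date | Start under 8.2 | TEAE from that start | TEAE under the 14.1 sentence |
|---|---|---|---|
| Missing, or after first dose | First-dose date | Yes | Yes |
| On the first-dose date | 1 January of that year | No | Yes |
| Before first dose | 1 January of the end year | No | Yes |

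(If first dose is itself on 1 January, the middle row gives Yes under both.) The conflict is confined to the last two rows. If 14.1 is read as meaning onset still unknown after imputation, its sentence has nothing to act on, because 8.2 supplies a start for every AE.

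**3. How often a partial start would be misclassified.** The documents give no number of partial dates, so this is a share of such AEs under stated assumptions. Take onset 1 to 28 days before first dose, end on any day from onset to the day before first dose, and first dose on each day of a 365-day year, all equally weighted.

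- Combinations: 365 × (1 + 2 + … + 28) = 365 × 406 = 148,190.
- *Day missing.* The event becomes a TEAE if its onset falls in the month of first dose. For first dose on day d of a month there are d(d − 1)/2 such combinations for d up to 28, and all 406 from d = 29. The sum over d = 1 to 28 is 3,654. A 31-day month gives 3,654 + 3 × 406 = 4,872, a 30-day month gives 3,654 + 2 × 406 = 4,466, and February gives 3,654. Total: 7 × 4,872 + 4 × 4,466 + 3,654 = 55,622, and 55,622 / 148,190 = 37.5%.
- *Day and month missing.* The event escapes only if its onset was in the previous calendar year: 28 × 406 − 3,654 = 7,714 combinations. So (148,190 − 7,714) / 148,190 = 94.8% become TEAEs.
- *Completely missing, under 8.2 alone.* 0%.

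**4. Effect on a table.** With the planned 41 per arm, one subject is 1/41 = 2.4 percentage points. SAP 14.1 also tabulates preferred terms that reach 5% in either dose group: 2/41 = 4.9% is out and 3/41 = 7.3% is in, so one misdated event can decide whether a term appears.

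**5. End dates.** Assume last dose on 12 September 2018, an AE starting on 20 September, and an end recorded as September 2018 without a day. Rule 8.2 gives an end of 12 September, 8 days before the start. TEAE status does not change, because it depends on the start only.

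**The case against.** The strongest defence is that assigning an uncertain onset to the first-dose date is a usual conservative convention, and that few events are involved. Onset and end dates must be documented (Protocol 6.2.1). Edit checks cover missing data and discrepancies within and across visits (SAP 6), and sites are queried (Protocol 9.1.1 and 9.2.1). A partial date for a screening AE can be queried at Day 1, at most 4 weeks later. On the conflict, 8.2 can be read as the operative rule because it says its dates serve to determine treatment emergence, which would make the sentence in 14.1 only a statement of the default.

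Most of this stands as a limit on size. It does not rescue the partial-start rules: conservatism applies when onset relative to dosing is uncertain, and a complete end date before first dose removes that uncertainty. On the conflict, the defence shows that a cross-reference would settle it, but the SAP contains none.

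A reader might go further in three ways that the documents do not support.

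- *That a reaction on the day of first dose is lost from the TEAE tables.* An event with unknown onset that ended on that day drops out only if 8.2 overrides 14.1. Under 14.1 it is kept, and the SAP does not say which governs.
- *That the end-date rules distort TEAE counts.* They do not. Status depends on the start, no AE-duration table is listed, and listings show original dates. An end before a start is a data-consistency fault.
- *That almost every safety table is affected.* SAP Section 19 lists 36 tables numbered 14.3. The 15 numbered 14.3.4 (acuity, imaging, examinations, pressure, vital signs, laboratory) do not use TEAE status, and two of the remaining 21 are titled as tables of serious adverse events.

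**Conclusion.** The partial-start rules are wrong as written. They classify as treatment-emergent some screening-phase AEs whose recorded end date shows that they were over before any exposure. Separately, 8.2 and 14.1 disagree on an AE with a completely missing start and an end on or before first dose, including one that ended on the day of first dose.

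The effect is small. One subject changes an arm's TEAE percentage by 2.4 points at most, assuming 41 treated per arm, and only if that subject has no other TEAE. The shares of 37.5% and 94.8% apply only to AEs with such partial dates and rest on the uniform-date assumptions above. The number of such AEs cannot be known from the documents and is probably low. The TEAE-based adverse event tables are affected. Efficacy and the other safety tables are not. This is a minor correction, but it concerns a stated rule that gives a wrong answer rather than a missing detail.

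**What to change.** - **(a) SAP 8.2, partial starts.** Keep both rules with their same-month and same-year conditions, and add: *unless the known end date is before the first-dose date, in which case impute the earliest date consistent with the recorded parts*. In the worked case the start becomes 1 June and the event is not a TEAE.
- **(b) SAP 8.2, completely missing start.** Change *on or before* to *before*, so that an event ending on the day of first dose keeps the first-dose date as its start.
- **(c) SAP 14.1.** State that an AE with unknown onset is treatment-emergent unless its end date is before the first-dose date. With (b), the two sections then agree in every row of the table above.
- **(d) SAP 8.2, end dates.** For consistency only, with no effect on TEAE counts: an imputed end date may never precede the start date.

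The conditions in (a) must stay. Take an ongoing AE with its start recorded as May without a day, and first dose on 20 June. It now gets 1 May and is correctly not a TEAE. A rule driven by the end date alone would move it to 20 June, against the recorded month.

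Once (a) is in place, the imputed start of an AE that ended before first dose cannot be later than its end if the recorded dates are consistent, so none of the cases in step 3 becomes a TEAE. The cost is a few lines of SAP text and programming, with no new data.

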8.3 Definition of Baseline

The baseline assessment will be the latest, valid pre-dose assessment available. Laboratory data may not be used from hemolyzed samples, mishandled samples, quantity not sufficient, or other conditions that would render the values invalid.

[figure not shown]
8.4 Data Analysis Conventions

All data analysis will be performed [REDACTED]. The final analysis will be performed after the study is completed and the database has been locked and released for unmasking. Statistical programming and analyses will be performed using SAS® Version 9.4 or higher.

Quantitative variables will be summarized using descriptive statistics including the number of observations (n), mean, SD, median, interquartile range (IQR), minimum, and maximum values. Means, medians, and confidence intervals (CIs) will be reported based on the level of precision for each variable. Summaries for discrete variables will include frequency counts and percentages. All percentages will be rounded to one decimal place (i.e., XX.X%). Change from baseline will be calculated as post-baseline value minus baseline value.

All efficacy analyses will be two-sided at a significance level of 0.05. The CIs for differences between treatment groups will be two-sided at 95% confidence. All p-values will be rounded to four decimal places; p-values less than 0.0001 will be presented as “<0.0001”; p-values greater than 0.9999 will be presented as “>0.9999.”

Extra assessments (i.e., unscheduled laboratory data or vital signs associated with non-protocol clinical visits or obtained in the course of investigating or managing AEs) will be included in listings, but not summaries. If more than one laboratory value is available for a given visit, the first valid observation will be used in summaries and all observations will be presented in listings. If the relative time is indeterminable, then the average of values at that visit will be used. It is noted that invalid laboratory data may not be used (from hemolyzed samples, mishandled samples, quantity not sufficient, or other conditions that would render values invalid).

8.5 Adjustments for Multiplicity

Adjustments for multiple treatment comparisons, analysis time points, and/or endpoints will not be made for this exploratory study.

9. Disposition of Subjects

Subject disposition will be presented in terms of the numbers and percentages of subjects who were screened, screen failures, randomized, randomized but not treated, completed the Week 16 visit (without rescue medication/procedure prior to the visit), completed the study, discontinued from the study, and rescued prior to the Week 16 visit. Subjects who are not discontinued from the study will be considered study completers. Disposition will be summarized by treatment group and for all enrolled subjects.

The number and percentage of subjects completing the study or who prematurely discontinued from the study and the reasons for study discontinuation will be summarized by treatment group for all randomized subjects. The reasons for study discontinuation prior to completion include: adverse event, use of rescue medication, subject compliance, withdrawal of consent, lost to follow-up, sponsor termination of study, positive pregnancy test, and other. A subject listing will be provided that includes the date of completion or discontinuation and reason for premature study discontinuation.

[figure not shown]
The number and percentage of subjects with protocol deviations will be summarized by treatment group for all randomized subjects. A subject listing will be provided that includes the start/end date of the deviation, the deviation description, deviation code, (informed consent, inclusion/exclusion and randomization, test article/study drug administration at site, improper protocol procedures at site, site failure to report serious adverse event (SAE)/AE, visit out of window, subject's use of prohibited concomitant medication, subject's failure to follow instructions, or other reasons) and the classification of whether the deviation was judged to be major or minor.

In addition, listings for all enrolled subjects will be provided that include informed consent date, randomization date/time, randomization number, inclusion and exclusion criteria violations, unmasking information, and exclusions from the FAS and PPS populations.

10. Demographic and Other Baseline Variables

10.1 Demographic Variables

Demographic and baseline characteristics will be summarized by treatment in the FAS and PPS populations.

The demographic variables collected in this study include age, sex, race, ethnicity, iris color, study eye, height, weight, and body mass index (BMI). Subjects who record more than one race will be grouped into a single category denoted as Multiple Race.

Age (years) will be summarized, by treatment, using descriptive statistics for continuous variables. Age will also be categorized as follows: <65 years and ≥65 years. Age will be reported in years and calculated using the following formula:

$$\text{Age} = (\text{Informed Consent Date} - \text{Date of Birth}) / 365.25, \text{ truncated as an integer}$$

The number and percentage of subjects will be presented, by treatment and over all subjects, for age category, sex, race, ethnicity, iris color, and study eye.

A subject listing that includes all demographic variables, including Screening physical examination findings, will be provided.

10.2 Baseline Disease Characteristics

Baseline disease characteristics will be summarized by treatment in the FAS and PPS populations.

[figure not shown]
Continuous summary statistics (n, mean, SD, median, IQR, minimum, maximum) will be presented for BCVA letter count at baseline, CST at baseline, time since DME diagnosis in the study eye, the estimated or total number of prior anti-VEGF injections administered in the study eye, CST prior to the first anti-VEGF injection, CST prior to each of the last three anti-VEGF injections, the estimated or total number of IVT steroid injections ever administered, and time since last IVT steroid injection.

Categorical summary statistics (counts and percentage) will be presented by treatment and over all subjects for the randomization stratification factors of visual acuity (Baseline BCVA: ≤55 Letters versus >55 Letters), CST (screening CST: ≤450 μm versus >450 μm), duration of DME (<6 months, 6 months-<1 year, 1 year-<2 years, 2 years-<3 years, ≥3 years), time since first anti-VEGF injection (<6 months, 6 months-<1 year, 1 year-<2 years, 2 years-<3 years), and time since last anti-VEGF injection (<6 months, 6 months-<1 year, 1 year-<2 years, 2 years-<3 years). The Snellen visual acuity prior to the first anti-VEGF injection, Snellen visual acuity prior to each of the last three anti-VEGF injections, and investigator assessment of edema and vision in the study eye compared to baseline after at least three anti-VEGF injections will also be summarized.

A listing of baseline disease characteristics will be produced.

11. Medical History and Prior and Concomitant Medications

Ocular and non-ocular medical history and prior and concomitant medications will be summarized separately by treatment in the FAS population.

11.1 Medical History

Medical history will be summarized using discrete summary statistics and presented by treatment group and over all subjects at the subject and event level by system organ class (SOC) and preferred term (PT), separately for ocular and non-ocular SOCs. If a subject reports the same PT multiple times within the same SOC, that PT will only be reported once within that SOC. As with the PT, if a subject reports multiple conditions within the same SOC, then that SOC will only be reported once. Separate tables will be created for ocular and non-ocular medical history. Medical history will be coded using Medical Dictionary for Regulatory Activities (MedDRA), version 20.1. The summaries will be based on the FAS population.

[figure not shown]
Listings of medical history will be generated separately for ocular and non-ocular SOCs.

